**Calendar 2: Maintenance BCG/Surveillance Schedule (+/- 3 weeks around each time point allowed)**

	Month 3*		Month 6		Month 9	Month 12		Month 18		Month 24	
	Cysto	BCG#	Cysto	BCG#		Cysto	BCG#	Cysto	BCG#	Cysto	BCG#
Required studies											
PHYSICAL											
History and physical	x		x			x		x		x	
Toxicity assessment		x		x			x		x		x
LABORATORY											
Dipstick urine	x	x	x	x		x	x	x	x	x	x
Urine cytology	x		x			x		x		x	
TESTS											
Cystoscopy	x		x		x	x		x		x	

\* after CR to BCG at 1st or 2nd induction course, # BCG is a 3 week course

## 14.0 MEASUREMENT OF EFFECT

For the purposes of this study, patients will be assessed for response at 3 months and 6 months. Continued response assessment during maintenance BCG will be as outlined by the study calendar above. Further imaging evaluation is as clinically indicated. Patients will be followed for a total of 2 years or 2 years following complete response.

### 14.1 DEFINITIONS

- **Recurrence/Residual disease**

Recurrent/residual urothelial carcinoma of the lower urinary tract is defined as any evidence of tumor by biopsy and/or urine cytology within the urinary bladder or prostatic urethra proximal to the striated urethral sphincter. Upper tract urothelial carcinoma (ureters, renal pelvis) does not constitute recurrent disease. Exam under anesthesia at the time of biopsy should be normal. If not consider 3-dimensional axial imaging to evaluate for progression.

- **Progression (to muscle invasive disease)**

This is defined as any tumor stage  $> T1$  found on scheduled repeat biopsy at 3 or 6 months and any biopsy performed thereafter. Locally advanced disease identified on 3-dimensional axial imaging as tumor extension into the perivesical fat will also constitute disease progression.

- **Metastases**

Evidence of disease outside the bladder (lymphadenopathy or metastatic site).

- **Urine Cytology**

- Negative Urine cytology constitutes a negative test result
- Positive Urine cytology constitutes evidence of disease
- Any finding other than negative or positive will be considered negative
  - An inadequate specimen will be repeated

- **Cystoscopic biopsy**

- In the absence of visible disease, random biopsies will be obtained at the discretion of the treating physician. Documentation of any urothelial carcinoma will constitute residual disease. Reactive changes, dysplasia, or other equivocal findings will be reviewed by the study team with the pathologist and treating physician to make a determination of residual disease. A completely negative biopsy will be considered no evidence of residual disease when combined with the results of the urine cytology study.
- Cystoscopic biopsy should include an exam under anesthesia- if the clinician reports a concerning finding on exam, this should be confirmed by imaging to document recurrent or progressive disease.

- **Exam under anesthesia**

- Normal: bladder mobile, no palpable bladder mass

- Abnormal may constitute any of the following
  - Fixed bladder
  - Palpable bladder mass
- **Findings on the prostate exam are not considered for normal or abnormal for the purpose of the study unless the clinician determines that abnormal prostate exam constitutes local extension of bladder cancer**
- **Imaging**
  - Follow-up imaging as clinically indicated.

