### 3. Primary Statistical Endpoint:

The primary endpoint of this phase II trial is to determine the complete response rate at 3 months as assessed by negative bladder biopsy, negative urine cytology, and normal exam under anesthesia of patients treated with a 6 week induction course of BCG followed by a 4-week course of **Sunitinib**.

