## 16.0 STATISTICAL CONSIDERATIONS

### 16.1 STUDY DESIGN/ENDPOINTS

The primary objective of this trial is to estimate the complete response rate in patients with high-risk non-muscle invasive bladder cancer treated with intravesical bacillus Calmette Guerin followed by daily oral sunitinib for 4 weeks as assessed by urine cytology, cystoscopic biopsy, and exam under anesthesia. If the response rate is 55% or less, there would be little interest in pursuing this therapy in further studies. In this case, we would like to terminate the trial early and consider a new therapy. If the response rate is 75% or more, further study would be proposed based on the estimates produced in this trial. To minimize the number of patients treated, the Minimax two-stage accrual design [Controlled Clinical Trials 10:1-10 1989] has been adopted.

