## [name], Phase II Study of BCG followed by Sunitinib for High risk NMIBC

We will accrue 24 high-risk non-muscle invasive bladder cancer patients. If less than 16 responses are seen, the trial will stop. If 16 or more responses are seen, an additional 12 patients will be entered. If 25 or more of the 36 evaluable patients achieve a complete response, then further studies will be proposed.

This trial design provides 80% statistical power at the 5% significance level. If the response rate was as low as 55%, there would be a 83% chance of stopping the trial after just 24 patients and only a 4.9% chance of going on to stage two (false positive error). However if the true response rate was 75%, there would only be a 12% chance of stopping the study early and a 19.9% chance of rejecting the therapy (false negative error). Evaluable patients will include all patients who receive at least one dose of sunitinib. Patients who are removed from the study before treatment with sunitinib will be replaced.

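### Complete response is scored more leniently than the stated endpoint: non-positive cytology counts as negative, equivocal biopsies are settled without criteria or masking, and no sensitivity analysis tests the 25-of-36 decision

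*Combined protocol and SAP*

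**What the plan says.** The Protocol Summary (Primary Statistical Endpoint) defines the 3-month complete response rate "as assessed by negative bladder biopsy, negative urine cytology, and normal exam under anesthesia". Section 1 uses the same three components.

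Section 14.1 then gives the working definitions. On cytology: "Any finding other than negative or positive will be considered negative". The one exception is an inadequate specimen, which is repeated. The table in 14.2 and the CR row in 14.3 carry this through as a combined negative-or-other category. CR in 14.3 also needs a negative cystoscopic biopsy and a negative exam under anesthesia, or negative imaging if the exam is positive.

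On biopsy, 14.1 lists reactive changes and dysplasia together with other unclear results, and says that such "equivocal findings will be reviewed by the study team with the pathologist and treating physician to make a determination of residual disease". No criteria, default, masking or tie-break is given. When no disease is visible, random biopsies are at the treating physician's discretion.

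Section 16.1 sets the test for this single-arm trial: "If the response rate is 55% or less, there would be little interest in pursuing this therapy in further studies". It adopts "the Minimax two-stage accrual design", with 24 patients first. "If less than 16 responses are seen, the trial will stop"; otherwise 12 more are entered, and 25 or more CRs among 36 lead to further studies. Section 16.2 reports the rate with a 95% confidence interval. Section 16.4.2 allows subanalyses that exclude patients with major deviations, but none that rescores equivocal results.

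**The concern.** A single-arm trial has no concurrent control that would be scored the same way. The CR count is set against a fixed 55%, so any leniency beyond what that benchmark used goes straight into the go decision.

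The two rules differ in kind. The cytology rule has a direction: a suspicious or atypical report cannot count against CR on its own. The biopsy rule has no built-in direction, but the plan leaves the call to people who know the treatment. They may also know the cytology result and the response tally. That last point is an inference: the documents describe no masking, but they do not say that the tally is shared, and the meeting topics in 17.3.1 do not list it.

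At stake is whether a result at or just above the threshold can be read as it stands. Under the present plan a reader of 25 of 36 could not tell whether it depended on equivocal calls.

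**Working it through.** **Inputs.** From 16.1: null rate p0 = 0.55, target p1 = 0.75; stage one n1 = 24, continue with at least 16 CRs; stage two adds 12; go with at least 25 of 36. The share of equivocal results and their scoring in the benchmark are not in the documents, so the shifts in step 2 are assumptions.

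**Formula.** With b(n, x, p) = C(n, x) p^x (1−p)^(n−x):

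- Early stop = sum of b(24, x, p) for x = 0 to 15.
- Go = sum over x = 16 to 24 of b(24, x, p) × P(Bin(12, p) ≥ 25 − x).

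**Step 1: reproduce the plan.**

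| True CR | Early stop | Go | Plan states |
|---|---|---|---|
| 0.55 | 0.827 | 0.0493 | 83%; false positive 4.9% |
| 0.75 | 0.121 | 0.8012 | 12%; false negative 19.9% (1 − 0.8012 = 0.1988) |

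All four figures reproduce.

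**Step 2: lenient scoring.** Suppose the true CR on the benchmark's scale is 55% and the trial's scoring adds d percentage points. The go formula is then evaluated at 0.55 + d. The equivalent share of true non-responders scored as CR is d / 0.45, and the expected number of extra CRs is 36 × d.

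| Assumed d | Scored rate | Share of non-responders | Extra CRs in 36 | False-positive rate |
|---|---|---|---|---|
| 0 | 0.55 | 0 | 0 | 4.9% |
| 1 point | 0.56 | 2.2% | 0.36 | 6.3% |
| 2 points | 0.57 | 4.4% | 0.72 | 7.9% |
| 5 points | 0.60 | 11.1% | 1.8 | 14.5% |

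**Step 3: how often would one patient decide?** 24/36 = 66.7% fails and 25/36 = 69.4% passes. If the concern is an over-generous score, the relevant result is exactly 25, where removing one CR reverses the decision. Its probability is the sum over x = 16 to 24 of b(24, x, p) × b(12, 25 − x, p):

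| True CR | P(exactly 25 of 36) |
|---|---|
| 0.55 | 2.4% |
| 0.65 | 9.9% |
| 0.70 | 11.6% |
| 0.75 | 8.8% |

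The stage-one gate is exposed in the same way: exactly 16 of 24, which is b(24, 16, p), has probability 8.7% at 0.55 and 16.8% at 0.65.

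**Step 4: what if equivocal results were failures in the primary count?** If 5% of true CRs were lost that way at a true 75%, the scored rate would be 0.75 × 0.95 = 0.7125 and power would fall from 80.1% to 63.4%. This is why the strict definition belongs in a sensitivity analysis and should not replace the primary rule.

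**The case against.** The strongest reply is that the cytology rule is not ad hoc. It is written down in advance, it is consistent across 14.1, 14.2 and 14.3, and it can be read as the operational meaning of negative in the endpoint. Other cytology alone never yields CR; the biopsy and exam must also be clear, and inadequate specimens are repeated. All of this stands. It does not show that the 55% benchmark was scored the same way, and it does not supply a rule for equivocal biopsies.

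A reader might infer that both rules favour CR. Only the cytology rule has a direction. Biopsy calls could go either way, and the pathologist takes part in them.

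A reader might also infer that the false-positive rate is in fact inflated. That needs two things the documents do not give: patients with other cytology who truly have disease, and a benchmark scored more strictly. If the benchmark was scored alike, there is no bias. There may also be some cushion: 55% is the top of the quoted 45–55% range, and at a true 50% the go probability is 1.25%, rising only to 4.9% after a 5-point shift. That cushion depends on case mix, since 2.1 and 2.3 quote up to 70% for carcinoma in situ.

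Finally, it is tempting to say that one patient decides about 19–20% of trials, by pooling results of 24 and 25 at a true CR of 65–70%. Upward bias concerns only an observed 25, and those rates are near the peak. Any fixed cutoff also has such a boundary. The figures in step 3 are the fair ones.

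**Conclusion.** The point holds as a moderate, inexpensive improvement. The scoring of CR is looser than the stated endpoint on cytology, undefined for equivocal biopsies, and not covered by any planned sensitivity analysis.

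The size is conditional. A false-positive rate of 6.3%, 7.9% or 14.5% in place of 4.9% rests on assumed leniency of 1, 2 or 5 points relative to the benchmark; the documents neither confirm nor exclude these values. The design arithmetic is sound and the thresholds need no change. Because a go result leads only to further studies and is reported with a confidence interval, this is something the sponsor should do; it does not invalidate the trial.

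**What to change.** 1. Keep the 14.1 cytology rule and the 25-of-36 rule for the primary count.
2. In 16.2, prespecify a strict-CR sensitivity analysis: cytology reported as negative, biopsy unequivocally negative, and every equivocal result counted as non-CR. The exam-and-imaging condition stays as in 14.3. Report whether the 16-of-24 and 25-of-36 thresholds are met under both definitions, and how many patients differ between them.
3. In 14.1, for endpoint scoring only, have the existing pathologist record each equivocal biopsy as residual disease or no residual disease, without the cytology result or the response tally. State a default for findings that remain equivocal. Decisions on further treatment stay as the protocol has them.
4. Align the endpoint wording in the Protocol Summary and section 1 with 14.3, so that the cytology rule is visible where the endpoint is stated.

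The cost is protocol wording and one analysis of data already collected, with no additional reader. The downsides are that the strict CR rate will be equal to or lower than the primary rate, and that the endpoint score may occasionally differ from the clinical determination.

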## 14.2 GUIDELINES FOR DOCUMENTING RESIDUAL DISEASE, RECURRENCE, PROGRESSION, OR METASTASES

### Residual/Recurrent disease

- **Will be assessed at 3 and 6 months, as clinically indicated (Exam under anesthesia should be normal- if not see progression)**

Urine cytology*	Cystoscopic Biopsy*	Determination
Negative/other	Negative	No residual disease
Negative/other	Positive	Residual disease
Positive	Positive	Residual Disease
Positive	Negative	Residual disease

*Abnormal exam under anesthesia of the bladder requires follow-up imaging*

### Disease progression or metastases: assessed at 3 and 6 months and as clinically indicated

Cystoscopic biopsy	Exam under anesthesia	Other Tests	Determination
Negative	Negative	N/A	No progression
Negative	Positive	Confirmation by repeat imaging, biopsy or other tests as above	If confirmation negative, then no progression, If +, then progression or metastases depending on location- see defns
Positive ≤ stage T1	Negative	N/A	Residual/recurrent disease, no progression
Positive ≤ stage T1	Positive	Confirmation by repeat imaging, biopsy or other tests as above	If confirmation negative, then residual/recurrent disease, If +, then progression or metastases depending on location-see defns
Positive > T1	Negative	Further imaging may be warranted at the discretion of the treating clinician	Progression
Positive > T1	Positive	Confirmation by repeat imaging, biopsy or other tests as above	Progression or metastases as defined by definition above

#### 14.3 RESPONSE CRITERIA

Complete Response (CR):	Negative/other urine cytology + negative cystoscopic biopsy, negative exam under anesthesia (if positive, imaging must be negative)
Residual Disease:	A positive cytology and/or a positive cystoscopic biopsy, negative exam under anesthesia (if positive, imaging must be negative)
Progressive Disease (PD):	A biopsy demonstrating > stage T1 bladder tumor. A positive exam under anesthesia confirmed by imaging constitutes progression.
Metastases:	A confirmed site of disease by definitions above of urothelial malignancy outside the bladder.

#### 14.4 DURATION OF RESPONSE

- Complete response assessed in every subject receiving at least one dose of sunitinib at 3 months. This will be determined as a percentage of the patients.
- Complete response will be assessed in all those patients undergoing a second cycle of BCG followed by SUNITINIB.
  - Those responding to an initial course and going to maintenance therapy will not be evaluated for CR at 6 months
  - Those patients unable to receive a second induction course of BCG followed by sunitinib will not be evaluated for CR at 6 months
- Recurrence free survival:
  - Recurrence definition as above
  - Assessed from time of study enrollment until recurrence or 2 years
  - Patients receiving a second induction course are assumed to have residual disease, not recurrence
    - Recurrence free survival is therefore assessed from study enrollment until recurrence or two years
  - Assessed in those patients with intact bladder only
  - Assessed only in those completing one induction course of BCG and receiving any sunitinib
- Progression free survival:
  - Progression definition as above
  - Assessed from time of study enrollment until progression or 2 years
  - Patients receiving a second induction course are assumed to have residual disease

- Progression free survival is therefore assessed from study enrollment until progression or two years
  - Assessed in those patients with intact bladder only
  - Assessed only in those completing one induction course of BCG and receiving any sunitinib
- Metastases free survival
  - Definition above
  - Assessed in those patients completing one induction course of BCG and any sunitinib
  - Assessed from time of study enrollment to disease or two years

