For those patients with adverse features including tumor recurrence, multifocality, invasion into the lamina propria, sessile architecture, mixed histology, high grade tumor, or tumors associated with carcinoma in situ, endoscopic resection is typically combined with intravesical therapy. There are a variety of current intravesical agents used in the management of non-muscle invasive bladder cancer. Mitomycin is a chemotherapeutic agent that is frequently instilled at the time of endoscopic resection. In several series, mitomycin has been shown to reduce the risk of recurrence when combined with endoscopic resection.[8] However, it does not appear to prevent disease progression which is the predominant factor in overall survival in this population. As a consequence several intravesical agents are used clinically in the peri-operative period to prevent tumor recurrence and progression. To date, the most effective agent is bacillus Calmette Guerin (BCG). In several randomized controlled studies in patients with non-muscle invasive disease, the average percentage of patients with complete response to intravesical chemotherapy was roughly 30% compared to 45-55% for those treated with BCG at 3 months. While the percentage of patients responding at 3 months with CIS is similar to other tumors using intravesical chemotherapy, up to 70% of patients treated with BCG will have a complete response at 3 months.[9] An expected 30% of patients failing initial induction with BCG will respond to a second

course of BCG. However, residual disease following two induction courses of BCG denotes a high risk of tumor progression.

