## 7.0 DURATION OF THERAPY

### 7.1 BCG

- Patients will receive within either 6 weeks of bladder biopsy or within 3 months of bladder biopsy and a cystoscopy within 6 weeks of enrollment confirming no visible tumor a 6 week course of BCG as described above.
- Please see section 10 for dosing delays and modifications. Patients unable to complete an induction course of BCG will be removed from the study and replaced with a new subject. The removed subject will be offered alternative treatment options.
- After completion of a 6 week course of BCG, patients will undergo a 2 week rest period before initiating sunitinib
- All patients will be assessed at 3 months after enrollment with repeat bladder biopsy done at the study institution and urine cytology regardless of completion of the study drugs as this is standard of care.
- Patients demonstrating residual disease at 3 months will receive a second complete cycle of the study drugs (BCG followed by sunitinib) if the tumor remains non-muscle invasive. However, patients may elect to proceed to alternative treatments if there is residual non-muscle invasive disease. Patients completing at least one cycle of the study treatment will be assessed for primary and secondary endpoints where applicable.
- Patients with evidence of muscle invasive disease on restaging bladder tumor biopsy will be withdrawn from the study and offered standard alternative treatment options.

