### 16.2 ANALYSES

The primary endpoint for this study will be the complete response rate. This rate will be reported along with 95% confidence intervals.

This study has several secondary endpoints. Response rates at 6 months will be reported with 95% confidence intervals for patients with an intact bladder. Kaplan-Meier estimates will be used to describe recurrence-free survival, including 2-year recurrence-free survival estimates. Toxicity of this therapy will be described, both overall and by grade. Toxicity rates will be tabulated by type and category.

Correlation of changes in VEGF, VEGFR, p53, and other cytokine expression to response will be explored. Markers will be grouped based on terciles of the distribution. Bivariate relationships between the expression level and response status will be assessed with the Mantel-Haenszel chi-square test. Potential analyses will include logistic regression with an outcome of response and Kaplan-Meier methods for time to recurrence. Differences in time to recurrence by expression level will be illustrated by Kaplan-Meier plots and tested using the log-rank test. Due to the sample size and the number of factors we will be statistically testing, these analyses will be considered exploratory until confirmed in a larger, independent, clinical trial.

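### Recurrence-free survival in 14.4 exempts tumour found at 3 months when the patient is re-treated, so patients with documented tumour are carried as recurrence-free from enrollment and the 2-year estimate depends on later treatment

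*Combined protocol and SAP*

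**What the plan says.** RFS at 2 years is a named secondary objective (Section 1). Five pieces of text fix what it measures.

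- **Event.** Section 14.4 refers back to the recurrence definition in 14.1, which treats recurrence and residual disease together: "Recurrent/residual urothelial carcinoma of the lower urinary tract is defined as any evidence of tumor by biopsy and/or urine cytology".
- **Exception.** The only exception in 14.4 is "Patients receiving a second induction course are assumed to have residual disease, not recurrence". Receiving treatment triggers it, not a different biopsy or cytology result.
- **Clock.** The start is not moved for re-treated patients: "Recurrence free survival is therefore assessed from study enrollment until recurrence or two years".
- **Analysis set.** "Assessed only in those completing one induction course of BCG and receiving any sunitinib", and "Assessed in those patients with intact bladder only". A CR is not required.
- **Analysis.** In 16.2, "Kaplan-Meier estimates will be used to describe recurrence-free survival, including 2-year recurrence-free survival estimates". No target rate, test of treatment effect or rule for non-responders is given.

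The second course is not automatic. Section 7.1 says: "However, patients may elect to proceed to alternative treatments if there is residual non-muscle invasive disease". The study calendar in Section 13 lists an alternative plan next to the second cycle. Section 7.2 and the ejection-fraction paragraph under 10.2.1 make the second cycle depend on the MUGA scan.

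**The concern.** An event definition should depend on what is found, not on what is done next. Here the 3-month finding is set aside when a second course follows. This has two consequences.

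First, the curve carries patients with biopsy- or cytology-documented tumour as recurrence-free, from enrollment, through the months when tumour was known to be present. If they clear later and stay clear, they count as recurrence-free for the full 2 years.

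Second, the estimate can move with the share of non-responders who are re-treated, which reflects patient preference, clinician preference and a heart scan as well as disease control. The intact-bladder condition adds a further link to later treatment, because a non-responder who goes to cystectomy may leave the set altogether.

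What is at stake is how the 2-year RFS can be read. It cannot be set beside an RFS from another source in which tumour at 3 months counts as failure. Section 2.5 gives possible improvement in RFS as a reason for trying to raise the early CR rate, so readers will look at it.

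**Working it through.** **The plan's own figures.** The plan states no figure for RFS. Its only computed design is the two-stage rule for 3-month CR in 16.1, which supplies the sample size and CR rates used here. An exact binomial calculation (24 then 36 patients; continue with 16 or more CRs; success with 25 or more) gives early stopping of 82.7% at a true rate of 55% and 12.1% at 75%, a false-positive rate of 4.9% and a false-negative rate of 19.9%. These agree with 16.1.

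**Inputs**

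- N = 36 evaluable patients (16.1).
- C = number of 3-month CRs: 20 (36 × 0.55 = 19.8), 25 (the success threshold) or 27 (36 × 0.75).
- M = N − C non-responders: 16, 11 or 9.
- s = 0.30, from Section 2.1: "An expected 30% of patients failing initial induction with BCG will respond to a second" course. This is for BCG alone and is borrowed for illustration.
- f = share of non-responders re-treated (assumption, 0 to 1).
- d = share of complete responders still tumour-free at 2 years (assumption, 0.6 to 1.0, the same after one or two courses).
- No censoring, so the Kaplan-Meier estimate equals a simple proportion. Non-responders who are not re-treated are counted as events, following 14.1 read with 14.4.

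**Just after the 3-month assessment.** If every 3-month tumour is an event, RFS equals C/N. Under 14.4 it is (C + fM)/N. With C = 25:

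- f = 0: 25/36 = 69.4%
- f = 0.5: (25 + 5.5)/36 = 84.7%
- f = 1: 36/36 = 100%

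The biopsy results are the same in all three. If patients who are not re-treated are exempt as well, the figure is 100% whatever f is, leaving aside any whose 3-month result is progression.

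**At 2 years**

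- Uniform rule (3-month tumour is an event for all): Cd/N.
- Text, reading A (a positive 6-month biopsy after the second course is an event): (Cd + fMsd)/N. Rise over uniform: fMsd/N.
- Text, reading B (that biopsy is still called residual and is not an event): [Cd + fM(sd + 1 − s)]/N. Rise: fM(sd + 1 − s)/N.

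With f = 1:

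| C | d | Uniform | A | Rise | B | Rise |
|---|---|---|---|---|---|---|
| 20 | 0.6 | 33.3% | 41.3% | 8.0 | 72.4% | 39.1 |
| 20 | 1.0 | 55.6% | 68.9% | 13.3 | 100% | 44.4 |
| 25 | 0.8 | 55.6% | 62.9% | 7.3 | 84.3% | 28.7 |
| 27 | 0.6 | 45.0% | 49.5% | 4.5 | 67.0% | 22.0 |
| 27 | 1.0 | 75.0% | 82.5% | 7.5 | 100% | 25.0 |

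For example, with C = 25 and d = 0.8, the uniform figure is 25 × 0.8/36 = 20/36. Reading A adds 11 × 0.30 × 0.8 = 2.64 patients, giving 22.64/36. With half re-treated, reading A gives (20 + 1.32)/36 = 59.2%.

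**Intact-bladder condition.** Take the same case (C = 25, d = 0.8, half re-treated), but suppose the 5.5 who are not re-treated have a cystectomy and leave the set. Reading A then gives 21.32/30.5 = 69.9% instead of 59.2%, with no change in anyone's disease. At the extreme, with 20 CRs and all 16 non-responders removed this way, RFS just after 3 months is 20/20 rather than 20/36.

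**The case against.** **The event status of patients who are not re-treated is inferred.** A reader might conclude that the protocol makes the same biopsy an event for a patient who declines and not for one who accepts. No sentence says so. The tables in 14.2 and the criteria in 14.3 label a positive 3-month result *residual disease* for everyone, and the exception in 14.4 could be read as restating that label for the group expected to be re-treated. This stands: the status of these patients is unsettled, not settled against them. It does not rescue the definition, because exempting them too puts more patients with tumour into the recurrence-free count.

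**A larger size is tempting.** Taking 45% to 25% of 36 as 16.2 to 9.0 non-responders and multiplying by 30% gives 4.9 to 2.7 patients, or 13.5 to 7.5 points. That is a ceiling. It assumes every non-responder can be re-treated, although 14.3 separates out progression and metastases and a second cycle needs an acceptable MUGA scan. It also assumes complete durability to 2 years and a response rate that belongs to BCG alone. Nor can one say that the distortion vanishes if everyone declines, since the intact-bladder condition can then raise RFS.

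**The strategy has up to two courses.** The summary's first secondary objective and its schedule describe a second course for residual disease. An RFS after up to two courses suits that strategy, and its exceeding the 3-month CR rate is not in itself an overstatement. The 3-month failures are not hidden either, since 3-month CR is the primary endpoint. This also stands, and it is why the present version should be kept and labelled rather than removed. Which curve leads is partly preference. But if residual disease is truly not recurrence, one would expect RFS to start at CR and be limited to responders, and 14.4 does neither. Section 3.1.1 also admits patients whose recent cystoscopy showed no gross disease, so calling their 3-month tumour residual is an assumption.

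**RFS is secondary and descriptive.** Correct, and this limits the weight of the point.

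**Conclusion.** The point holds in a limited form. As written, 14.4 carries re-treated patients with documented 3-month tumour as recurrence-free from enrollment, leaves the status of other non-responders to inference, and lets later treatment, including cystectomy, influence the estimate. Neither reading of the patients who are not re-treated removes the problem.

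Under the assumptions set out above, with all non-responders re-treatable and re-treated and a positive 6-month biopsy counted as an event, 2-year RFS is about 4.5 to 13.3 points higher than if 3-month tumour were an event. If a positive 6-month biopsy is still called residual, the rise is about 22 to 44 points. A reader might infer that patients who never clear are certainly counted as recurrence-free. The documents do not establish that, because they do not say how such a biopsy is classed for RFS. Durability and the re-treated share are assumptions, so these figures show scale and are not predictions.

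The primary endpoint, the sample size and the go/no-go rule are not affected. The change should be made before RFS is analysed.

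**What to change.** In 14.4 and 16.2:

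1. Report an RFS in which the first tumour found at or after the 3-month assessment is an event, for every patient who completed one BCG induction course and received any sunitinib, whether or not re-treated.
2. In that version, a patient with 3-month tumour who later has a cystectomy keeps the 3-month event and stays in the set.
3. Report the present version beside it, labelled as RFS after up to two induction courses, with one stated rule for re-treated and non-re-treated patients alike. The rule should also say how a positive 6-month biopsy is classed.

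The cost is a few lines of text, one extra Kaplan-Meier curve and a less favourable RFS figure to report. No new data are needed, because 7.1 already requires the 3-month biopsy and cytology for all patients. Treatment is unchanged.
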